#### VALIDATION

Information on the quality of recording of vaccinations will be obtained from the ADVANCE fingerprint (quality assessment) data by comparing coverage estimates from the databases with WHO/national coverage rates in the same age range.

### 7.2.7.2. Outcomes, Operationalization and Validation

#### OUTCOMES

The safety outcomes of interest are known reactions:

- Injection site reactions: erythema, edema, induration/ nodule/sterile abscess, pain/tenderness
- Fever
- Somnolence

- 
- Persistent crying, irritability
  - Generalized convulsions
  - HHE
  - Extensive limb swelling

A definition for somnolence is provided in Appendix 3. The Brighton Collaboration has case definitions available for injection site reaction [18], fever [19], persistent crying [20], generalized convulsions [21], HHE [22], and swelling (i.e. swelling at or near injection site as an increase in size or volume at the injection site that may extend to the entire limb according to severity) [23].

Events will be extracted from the electronic health care databases as diagnosis codes or text or by means of proxies. Mapping to ICD-9/10, READ and ICPC codes will be done semi-automatically using the ADVANCE code mapper. Algorithms for identification will be created with the databases and benchmarked against external sources and within consortium as described in section 7.1.

### **VALIDATION**

Verification of the extracted codes and proxies for extraction of events will be done as part of the quality assessment and harmonization process (fingerprinting) prior to the start of the POC feasibility study. The verification will be done by comparing age-specific incidence rates between databases and comparison against external sources such as literature or other publicly available data. If possible, positive predictive values and sensitivity from prior studies will be retrieved. No chart validation at the patient level is foreseen for this POC feasibility study.

#### **7.2.7.3. Other Variables and Operationalizations**

The incidence rates will be stratified by age, sex, calendar time and country which will also allow for rolling back the benefit-risk model to look at the impact of sequential monitoring.

#### **7.2.8. Data Analysis**

##### **7.2.8.1. Statistical Hypothesis**

The purpose of the current POC feasibility study is to provide incidence rates of safety events observed after administration of wP and aP vaccines. There is no null hypothesis being tested in this study.

Since there is no formal hypothesis testing, there is no need for power and sample size calculation. The databases currently involved in ADVANCE capture 34 million persons, the population aged 0-6 may be between 5-8 million, even if event rates are low, enough cases should occur to estimate incidence rates. If stratification leads to zero numerators, higher level aggregation will be conducted.

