## VACCINE RISKS

### Safety Studies

In a study including 15,752 doses of diphtheria, tetanus, whole cell pertussis (DTwP) vaccine and 784 doses of diphtheria, tetanus (DT) vaccine performed in the Los Angeles area in 1978-1979, local redness, swelling and pain occurred in 37.4%, 40.7% and 50.9% of DTwP recipients compared with 7.6%, 7.6% and 9.9% of DT recipients, respectively. Frequencies increased in subsequent doses. Frequency of fever ( $\geq 38^\circ\text{C}$ ) was 46.5% and 9.3% after DTwP and DT, respectively. Furthermore, high-pitched unusual crying, convulsions and HHE following DTwP were reported in 0.1%, 0.06% and 0.06% recipients, respectively. Those events were not reported after DT, probably due to the low number of DT vaccinees [3].

---

A large study, performed in the USA, assessed common reactogenicity of 13 candidate aP vaccines compared to wP vaccine. For all adverse events following immunization (AEFIs), frequencies after aP vaccines were lower than after wP vaccines. For fever ( $\geq 37.8$  °C) frequency was 4.2% after the first dose of aP vaccine compared with 27.3% following wP vaccination. Temperature increased after subsequent doses. Incidence of local redness was 13.5% and 49.4%, local swelling was 8.7% and 39.7%, and local pain was 3.8% and 27.3% after aP and wP vaccination, respectively [10].

For rarer and more severe AEFIs, frequencies also differed. Persistent crying, very high fever ( $\geq 40.5$  °C), HHE and seizures were respectively 7, 7, 17 and 6 times more likely after vaccination with wP compared with aP [11].

In a large (n=28,796) questionnaire study carried out in the Netherlands between 2004 and 2007, frequencies of rarer, more severe AEFIs were higher after the Dutch wP vaccine (used until 2005) compared with the aP vaccine (introduced from January 1st 2005 onwards) [12]. In total, 1.5% of the infants reported prolonged crying  $\geq 3$  hours after first dose at two months after wP vaccination compared with 0.4% after aP. Frequencies of very high fever ( $\geq 40.5$  °C) after the fourth dose of wP and aP vaccines at 11 months were 0.8% and 0.2%, respectively, whereas frequencies for febrile convulsions after the fourth dose were 0.06% and 0.02%, and for HHE after the first dose were 0.12% and 0.03%, respectively.

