## **6. RESEARCH QUESTION AND OBJECTIVES**

The overall ADVANCE POC question is to test the currently available system for benefit-risk monitoring of vaccines in Europe. There will be several system testing methods, using the following question: Has the initial benefit-risk profile in children prior to school-entry booster been maintained after the switch from wP to aP pertussis vaccines?

The objectives of this specific POC feasibility study, which focuses on the incidence rates of safety outcomes of pertussis-containing vaccines, are:

- 
1. To evaluate participating databases on quality criteria for inclusion in the study (i.e. vaccination data on pertussis vaccine available, at least one of the outcomes available, data access and clearance of protocol possible within timelines of the POC feasibility study)
  2. To provide information that feeds into the benefit/risk model. The safety information required for the model is:  
Incidence rates of specific events (i.e. injection site reactions, fever, somnolence, persistent crying, irritability, febrile or afebrile seizure/convulsion, HHE, extensive limb swelling)
    - a) within specific risk windows after each dose of wP and aP vaccines in pre-school children
    - b) during the period outside the risk windows before and after each dose of wP and aP vaccines in pre-school children.
    - c) Over calendar time, to allow for analysis that will focus on sequential monitoring of B/R
  3. To provide calendar time specific incidence data as test for method development in ADVANCE WP4.

---

[figure not shown]

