### 7.2.8.3. Statistical Methods

#### COHORT STUDY

The incidence rate of each event will be calculated using a dynamic cohort approach. For each person in the cohort, follow-up time will be classified by calendar year, sex, age in year of birth and months and the different risk window (see exposure section). This persontime will be the denominator for the incidence rate calculations. Incidence rates will be calculated stratified by:

1. type of vaccine: wP/aP
2. database, country
2. dose of wP/aP (actually received dose)
3. risk window
4. age in months and year of birth
5. calendar year

[figure not shown]
Cases will be counted in the numerator for the rate calculation if the date of onset/occurrence of an event falls into the specific window of that vaccine, and will be further stratified to count in the correct age/sex and calendar year category at the date of onset.

A Poisson distribution will be used to calculate 95% CIs.

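### Aggregating only when a stratum shows zero events makes the reporting level depend on the outcome, and can bias aP and wP rates unequally in a direction the protocol leaves open

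*Protocol*

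**What the plan says.** Section 7.2.8.1 declares that no hypothesis is tested and relies on database size: "the population aged 0-6 may be between 5-8 million, even if event rates are low, enough cases should occur to estimate incidence rates". It then gives the rule for sparse cells: "If stratification leads to zero numerators, higher level aggregation will be conducted". Nothing in the protocol states which dimensions may be merged, in what order, whether only the empty cell or its whole level changes, or whether aP and wP may be combined.

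The cells are fine. The cohort part of section 7.2.8.3 begins "Incidence rates will be calculated stratified by" and lists vaccine type, database and country, dose, risk window, "age in months and year of birth", and calendar year; the surrounding text and section 7.2.7.3 add sex. The same section states: "A Poisson distribution will be used to calculate 95% CIs".

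The rates feed the effects table of the benefit-risk model (section 7.3.1, Table 6). Objective 2(c) in section 6 also asks for them "Over calendar time, to allow for analysis that will focus on sequential monitoring of B/R".

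**The concern.** A rule that looks at the numerator before choosing the level of reporting is outcome-dependent. If cells with events keep their own rate and empty cells borrow one from a coarser level, low results are raised and high results are left alone, so rates drift upward. The drift is larger for whichever vaccine has more empty cells, and this can distort the aP-wP comparison that the study supplies to the benefit-risk model.

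The rule is also unnecessary. A stratum with known person-time and no events already has a valid estimate of zero, and an exact Poisson interval exists for it. Replacing it discards information that sequential monitoring could use.

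**Working it through.** The protocol gives no figure for the effect of this rule, so there is none to reproduce. The check asks what the rule does under the readings its wording allows.

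**Inputs.** Section 5 (Safety Studies) cites a Dutch questionnaire study with HHE after dose 1 in 0.12% (wP) and 0.03% (aP), a ratio of 4. It also reports that "febrile convulsions after the fourth dose were 0.06% and 0.02"%, a ratio of 3. Doses per cell, n, are an **assumption**: the protocol gives neither cell sizes nor a wP:aP ratio. Only the product of n and the event probability p matters, so incomplete capture in a database acts like a smaller cell.

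**Step 1: empty cells.** P0 = exp(−n·p). For HHE with n = 2,000:
- aP: exp(−0.6) = 0.549
- wP: exp(−2.4) = 0.091

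**Step 2: only empty cells take the within-vaccine aggregate.** Unaltered cells average p. Overwriting the empty ones adds about P0·p, so the mean is p(1 + P0). The ratio becomes 4 × (1 + P0 for wP) divided by (1 + P0 for aP). At n = 2,000 it is 4 × 1.091 divided by 1.549, which is 2.82.

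| Doses per cell | P0 | HHE ratio (true 4) |
|---|---|---|
| aP 100, wP 100 | aP 0.970, wP 0.887 | ratio 3.83 |
| aP 1,000, wP 1,000 | aP 0.741, wP 0.301 | ratio 2.99 |
| aP 2,000, wP 2,000 | aP 0.549, wP 0.091 | ratio 2.82 |
| aP 5,000, wP 5,000 | aP 0.223, wP 0.002 | ratio 3.28 |
| aP 10,000, wP 10,000 | aP 0.050, wP <0.001 | ratio 3.81 |
| aP 2,000, wP 1,000 | aP 0.549, wP 0.301 | ratio 3.36 |
| aP 2,000, wP 500 | aP 0.549, wP 0.549 | ratio 4.00 |
| aP 2,000, wP 200 | aP 0.549, wP 0.787 | ratio 4.61 |

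For febrile convulsions at 2,000 doses per cell, the ratio of 3 becomes 3 × 1.301 divided by 1.670, which is 2.34.

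**Step 3: where the sign changes.** The two vaccines are inflated equally when n·p is equal, that is, when the wP cell is p(aP) divided by p(wP) times the aP cell: 0.03 divided by 0.12, or 1/4, for HHE and 0.02 divided by 0.06, or 1/3, for febrile convulsions. Below that fraction the contrast widens.

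**Step 4: other readings.**
- *A whole level is collapsed within vaccine type, or merged cells are weighted by person-time.* Total events over total denominator are unchanged, so there is no bias. Simulation with 50 strata per vaccine and 4,000 replicates gave HHE ratios of 3.98 to 4.03 for every cell size tried.
- *Empty cells borrow a pooled aP+wP rate.* At 2,000 doses the pooled rate is 7.5 per 10,000. Then aP is 3 + 0.549 × 7.5 = 7.1, wP is 12 + 0.091 × 7.5 = 12.7, and the ratio is 1.78.

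**Step 5: a zero needs no replacement.** The exact 95% upper limit for zero events is −ln(0.025) = 3.69 events. For 2,000 doses that is 3.69 divided by 2,000, or 0.18%.

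**The case against.** The strongest reply is that aggregation ordinarily means merging strata or dropping a level, and done that way within vaccine type it leaves the ratio intact. The figures near 3 need empty cells overwritten while their neighbours keep their own rates, and the protocol describes no such step. This stands as a limit on the claim. It does not clear the sentence, which permits either reading.

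A reader might infer that the rule falls harder on aP, inflates aP rates and so shrinks the contrast. The documents do not support that. It presumes roughly equal cells for the two vaccines, and no sizes are given. Section 7.2.9 expects few databases with wP data, and section 7.2.5 removes person-time around the switch. Neither fixes the size of a wP cell, but equality cannot be presumed. Where wP is not captured, its rate is a self-controlled case series ratio multiplied by a baseline rate, so comparing cell with cell does not describe that situation.

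Three further points hold in part:
- For risk-window rates, Table 6 needs country, year of birth, outcome and dose, not sex, month of age or calendar year. Its cells are larger than the finest strata, and the effect there may be smaller.
- Person-time denominators are kept, and section 7.3.2 lists monthly event rates for monitoring. Event-free strata may therefore be merged away, but it cannot be said that they will disappear.
- A merging order can properly be left to the analysis plan, to which section 7.2.12 refers. A plan that followed the protocol would still inherit the zero-event trigger.

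Section 7.2.9 also says that the results test a system and may not be the best estimates. That lowers the stakes but does not make the rule sound.

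**Conclusion.** The point holds in a limited form. The protocol fixes an outcome-dependent trigger and leaves its operation open. Depending on how it is applied, the HHE ratio of 4 could stay at 4, fall to about 2.8 (equal cells of 2,000 doses, only empty cells replaced), fall to 1.78 (replacement by a rate pooled over both vaccines), or rise to 4.61 (wP cells of 200 against aP cells of 2,000). All these sizes rest on assumed doses per cell and on the cited questionnaire frequencies. The effect is small for common events and for very small or very large cells. Neither its direction nor its size can be read from the protocol.

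Whichever reading applies, an observed-zero trigger can leave aP and wP reported at different granularity, and can remove event-free strata that objective 2(c) may need. Because no hypothesis is tested, no error rate or power statement is affected. The sentence should nevertheless be changed, since a better rule is available at little cost.

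**What to change.** Replace the sentence in section 7.2.8.1 with:

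> The aggregation level for each outcome and database is set from person-time or expected events (literature rates), not from the observed wP/aP stratum counts. It is the same for wP and aP where both are observed, and wP and aP are never merged. Strata with zero events are reported as 0 with their person-time and the exact Poisson 95% upper limit (3.69/person-time), and are passed to the benefit-risk model with that uncertainty.

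The condition refers to wP/aP stratum counts and not to all event data, because section 7.2.7.2 already has age-specific event rates compared across databases before the study starts.

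The change takes a few sentences and no new data. The threshold for person-time or expected events can go in the analysis plan. The downside is that some cells will show 0 with a wide upper limit: at 2,000 doses, 0.18%, which is above the 0.12% cited for HHE after wP. The benefit-risk model must accept a zero with an interval as an input.

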##### **7.2.8.2. Analysis of Demographics and Baseline Characteristics**

The population of subjects meeting the study population (i.e. cohort) inclusion criteria will be described in terms of the following variables. Continuous variables will be described as means, medians (i.e. follow-up time) and standard deviations, while categorical variables will be described as frequencies and percentages:

- age and sex at study population (i.e. cohort) entry, age at D1, D2, D3, D4, D5 by country, follow-up time in the cohort by calendar year and month, dose and age (year of birth), number of pertussis vaccine doses per child.

---

### 7.2.8.3. Statistical Methods

#### COHORT STUDY

The incidence rate of each event will be calculated using a dynamic cohort approach. For each person in the cohort, follow-up time will be classified by calendar year, sex, age in year of birth and months and the different risk window (see exposure section). This persontime will be the denominator for the incidence rate calculations. Incidence rates will be calculated stratified by:

1. type of vaccine: wP/aP
2. database, country
2. dose of wP/aP (actually received dose)
3. risk window
4. age in months and year of birth
5. calendar year

[figure not shown]
Cases will be counted in the numerator for the rate calculation if the date of onset/occurrence of an event falls into the specific window of that vaccine, and will be further stratified to count in the correct age/sex and calendar year category at the date of onset.

A Poisson distribution will be used to calculate 95% CIs.

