Study Design: The main study design is a retrospective dynamic cohort study. The study will be conducted utilizing electronic health care data from ADVANCE partners in different countries (i.e., Short descriptions of databases in respective countries and their full names will be included in this protocol upon final decisions of inclusions). In databases that cover the period in which wP was still provided, the incidence rate (IR) ratio for wP versus baseline risk will be calculated using a self-controlled case series (SCCS) design. This IR ratio will be applied to baseline rates for the aP period in databases that do not capture the wP period, to estimate the rate of events during wP in each specific database.			
Population: The study population will comprise all children registered in any of the participating databases during the study period and for whom an adequate start and end of follow-up and date of birth can be defined. Children will be followed from start of the study period, one month after date of birth (i.e. to allow for pre-vaccination time for the SCCS design and to avoid pre-term related or birth-induced increase in incidence rates), or date of valid data in the database (whichever is the latest) until the end of study period (31-12-2015, the school-entry pertussis booster, transferring out of the database, death, reaching age 6 years: whichever is the earliest).			

**Variables:***Exposure of interest*

Any wP vaccines and aP pertussis-containing vaccines and their doses in the vaccine schedule (D1, D2, D3, D4, D5)

*Outcomes*

- Injection site reactions: erythema, edema, induration/nodule/sterile abscess, pain/tenderness
- Fever
- Somnolence
- Persistent crying, irritability
- Generalized convulsive seizures
- HHE
- Extensive limb swelling

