**Data Sources:**

- Electronic health care databases (record linkage, surveillance and GP-based databases) currently available in the ADVANCE consortium and eligible are located in Denmark, Spain, Italy, The Netherlands and UK. Short descriptions of databases and their full names will be included in this protocol upon final decisions of inclusions.

**Study Size:** Total population (0-6 year of age) of all eligible ADVANCE databases

**Data Analysis:** The purpose of this study is to provide incidence rates (i.e. baseline and risk-window specific) of known adverse reactions following vaccination with pertussis-containing vaccines for use in a multi-criteria decision analysis (MCDA) model of benefits and risks of wP versus aP pertussis vaccines (models are described in a separate benefit-risk study protocol). In some more recent databases, wP information will not be captured. To generate risk-window specific incidence rates for the wP period in these databases, the IR ratio originating from an SCCS analysis of wP versus baseline in other databases will be multiplied by the baseline IR.

**Informed Consent and Ethical Approval:** This study will be conducted on the basis of secondary use of electronic healthcare records. Each database will apply local governance and privacy rules prior to aggregating and sharing anonymized data.

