#### EXPOSURE WINDOWS

Person time of follow up in the cohort will be categorized as risk and baseline periods. Persons will be followed up over the whole period independent of occurrence of an event or vaccination. Person time will not be stopped at the occurrence of an event or vaccination. The vaccination day and outcome-specific risk-windows after vaccination will be classified as risk periods, and the period between the end of the risk-window after vaccination until the next pertussis-containing vaccination or end of follow-up as the baseline period. To keep track of dose, these periods will also be labelled by the number of previous pertussis-containing vaccinations.

---

Outcome	Risk Window After Vaccination
Injection site reactions	0-7 days
Fever	0-72 hours
Somnolence	0-48 hours
Persistent crying, irritability	0-24 hours
Generalized convulsions	0-72 hours
HHE	0-48 hours
Extensive limb swelling	0-7 days

---

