### 7.2.9. Limitations

In this POC feasibility study that tests and evaluates the ADVANCE system, tailored to generate rapid evidence on vaccine effects, there are several methodological limitations. These limitations will be assessed, and are an integral part of the system evaluation process. The following points are considered to be the expected limitations:

- Given that this POC feasibility study evaluates a system and its different processes, the epidemiological results produced (i.e. incidence rates and risk ratios) should not be considered as evidence that can be directly translated to inform epidemiological and pharmacovigilance decision-making processes. The epidemiological results produced in this POC feasibility study are part of a set of evaluation indicators to test the ADVANCE system and may not be the best or true estimates
- It could be possible that within the process of database selection it will become evident that proposed case definition(s) for the events are either different, or are differently interpreted, in a specific database or country. Different countries and databases could be using different case definitions. To address this limitation, the study will produce country-and database-specific analyses and results.
- Some event outcomes are signs and symptoms and not disease entities. The coding in databases might not be applicable to signs and symptoms (e.g. crying). Therefore, database extraction algorithms and strategies need to be adapted (e.g. include also free text search).
- Event codes in databases might contain the whole spectrum of potential, probable and confirmed cases. Given the POC feasibility study nature to test the system and to save costs and time, diagnostic codes will not be validated on a patient level using medical histories and charts.

- 
- It is expected that only a limited number of databases will have information on wP vaccination available. Therefore, the suggested strategies in the methods sections 7.4.3 (i.e. multiplying baseline incidence rates with IR ratios across databases, time periods, and wP/ aP data) will be applied. The additional use of literature information will be carefully evaluated and interpreted.
  - The type of database used (e.g. GP database, hospital database, claim database, etc) will influence incidence rates. To address this limitation, the study will produce country/ database-specific analyses and results.

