### **7.2.10. Study Size**

There is no target sample size for this study. The sample size is determined by the study population in the ADVANCE databases, which currently accumulates to more than 34 million subjects and 314 million person-years. The actual size available to estimate incidence rates of safety outcomes after vaccination may diminish if databases do not have good quality data on the vaccinations, which is part of the study assessment.

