#### 7.3.1. Benefit/risk analysis

This POC study will yield incidence rates (during exposure window and after exposure window) plus relative risk estimates that will be used in the B/R analysis.

**Table 6: Evidence Required for Safety Outcomes to Build the Effects Table by Country, Year of Birth and for Each Outcome in the B/R analysis**

Incidence in risk period after wP or aP vaccination						
Time since dose**	Dose 1*		Dose 2		Dose 3	
	Inc	95% CI	Inc	95% CI	Inc	95% CI
Risk window 1						
Risk window 2						
Risk window 3						
Baseline incidence						
2-3 months						
3-4 months						
4-5 months						
...						

\* number of doses might depend on the country and year

\*\* risk windows might be different depending on the safety outcome

In addition, the relative risk estimate from the SCCS will be used as described in the analysis

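### The protocol's one interval rule, a plain Poisson 95% CI, has no term for the SCCS ratio's error in extrapolated wP rates or for repeat events in one child; intervals built on it would be too narrow

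*Protocol*

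**What the plan says.** The interval rule closes the cohort part of Section 7.2.8.3: "A Poisson distribution will be used to calculate 95% CIs". It follows the rule that cases enter the numerator by date of onset or occurrence. The document states no other interval rule for rates.

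Where a database has no wP data, the Abstract (Data Analysis) says that "the IR ratio originating from an SCCS analysis of wP versus baseline in other databases will be multiplied by the baseline IR". The Abstract's study design entry says the same: "This IR ratio will be applied to baseline rates for the aP period in databases that do not capture the wP period". Section 7.2.1 repeats the approach. Section 7.2.9 shows that it will be used often: "It is expected that only a limited number of databases will have information on wP vaccination available". The SCCS part of Section 7.2.8.3 names conditional Poisson regression for the ratio, but no interval for the ratio or for the product.

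Table 6 in Section 7.3.1 has a block headed "Incidence in risk period after wP or aP vaccination", with an incidence and a 95% CI for each dose.

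On follow-up, Section 7.2.7.1 (Exposure windows) says: "Person time will not be stopped at the occurrence of an event or vaccination". There is no first-event rule, episode rule or gap between events.

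**The concern.** An extrapolated wP rate is the product of two estimates and not a count, so the stated rule cannot supply the interval that Table 6 requires. Applied to the local baseline count, it leaves out the error of the ratio. That error will often be the larger one, because the ratio rests on the few databases with wP data, while baseline time is plentiful. The omission can only make the interval narrower. Every database that borrows the ratio also shares its error, and this should be visible in the output.

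The second part is milder. A plain Poisson interval treats the events behind a rate as independent. If counting continues after an event, one child can supply several correlated events. This matters mostly for baseline rates, because baseline time runs for months and the risk windows last days. If revisits for one episode were recorded as new events after the window, they would also fall into the SCCS post-window baseline and pull the ratio toward 1.

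At stake is the stated precision of the wP side of the comparison that goes into the benefit-risk analysis.

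**Working it through.** The plan has no figure to reproduce: "There is no null hypothesis being tested in this study" (Section 7.2.8.1) and "There is no target sample size for this study" (Section 7.2.10). No event counts or interval widths are given. The direction follows from the method. The sizes below rest on assumed inputs.

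**Extrapolated wP rate**

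From the documents (Sections 7.2.5 and 7.2.7.1):
- The 0-72 hour window, counted in days with day 0 included, is 4 days.
- The SCCS baseline is days -31 to -8 (24 days) plus days 4 to 31 (28 days), or 52 days per dose. Overlap between closely spaced doses is ignored.

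Assumed: true ratio R of 3 or 6; total SCCS cases n from 20 to 1,000; local baseline events d from 100 to 10,000.

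The two estimates come from different databases, so their variances add on the log scale:
- Share of SCCS cases in the risk window: p = 4R / (4R + 52)
- var(log IRR) = 1/(np) + 1/(n(1-p))
- var(log rate) = 1/d + var(log IRR)
- A Poisson interval on the local count uses 1/d alone.
- Its true coverage is 2Φ(1.96/k) - 1, where k is the full standard error divided by the Poisson-only one.

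Example with R = 6, n = 200, d = 1,000:
- p = 24/76 = 0.316, giving 63.2 risk and 136.8 baseline cases.
- var(log IRR) = 1/63.2 + 1/136.8 = 0.0231.
- Poisson-only: 1.96 × √0.001 = 0.062, limits ×/÷ 1.06.
- Both errors: 1.96 × √0.0241 = 0.304, limits ×/÷ 1.36.
- k = 4.9, coverage 31%.

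| R | SCCS cases | Baseline events | Poisson-only limits | Limits with both errors | k | Coverage |
|---|---|---|---|---|---|---|
| 6 | 1,000 | 100 | ×/÷ 1.22 | ×/÷ 1.27 | 1.2 | 90% |
| 6 | 200 | 1,000 | ×/÷ 1.06 | ×/÷ 1.36 | 4.9 | 31% |
| 3 | 200 | 1,000 | ×/÷ 1.06 | ×/÷ 1.43 | 5.8 | 26% |
| 3 | 20 | 10,000 | ×/÷ 1.02 | ×/÷ 3.07 | 57 | 3% |

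The first and last rows are the extremes of the grid examined. Age and season terms and between-database variation are left out; between-database variation would widen the correct interval further.

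**Repeat events in a directly counted rate**

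Assume that a share q of affected children have two events in the same stratum and the rest have one. The variance inflation is E[K²]/E[K] = (1 + 3q)/(1 + q). Coverage of the exact Poisson interval was simulated with 50 affected children expected and 20,000 runs.

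| q | Variance inflation | Needed widening | Coverage |
|---|---|---|---|
| 10% | 1.3/1.1 = 1.18 | 1.09 | 94% |
| 30% | 1.9/1.3 = 1.46 | 1.21 | 90% |
| 50% | 2.5/1.5 = 1.67 | 1.29 | 87% |

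With heavy repetition (geometric, mean of 2 events per affected child) the inflation is 3, the widening 1.73 and coverage about 75%.

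**Revisits in the SCCS baseline, if they were counted**

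Assume a true ratio of 5, with 20% of risk-window episodes having one later record in the post-window baseline. Repeats of baseline episodes are left out.
- Days 0-3: 5 / ((52 + 0.2 × 4 × 5)/52) = 4.6.
- Days 0-7 (8 risk days, 24 + 24 = 48 baseline days): 5 / ((48 + 0.2 × 8 × 5)/48) = 4.3.

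**The case against.** The Poisson sentence stands under the cohort heading, where it is a usual choice for counted events. Extrapolation falls under the SCCS heading, and nothing applies the Poisson rule to the product. A reader might infer that the protocol decides to ignore the ratio's error. It does not: it is silent. Conditional Poisson regression will supply a standard error for the ratio, Section 7.2.12 refers to a statistical analysis plan that is not at hand, and Figure 4, which sets out the extrapolation, could not be seen. All this stands, and it makes the point conditional. It does not remove it, because the one stated rule cannot yield an interval that the protocol itself requires.

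Three further readings go too far:
- That every revisit in a window counts as a new event. Section 7.2.8.3 counts cases by onset or occurrence, and the extraction algorithms may merge records. Continued follow-up still allows several true events per child.
- That extrapolated wP rates would appear to agree across countries because they share a ratio. Each rate is that ratio times a local baseline, and Section 7.2.9 expects the type of database to influence the rates. Only the ratio and its error are shared.
- That the benefit-risk model takes these intervals as its whole uncertainty. Section 7.3.1 also hands over the SCCS relative risk, and how the model uses it belongs to the separate benefit-risk protocol.

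Nor is the baseline error always the smaller one. Rates are finely stratified, and with 100 baseline events and 1,000 SCCS cases the loss of coverage is modest.

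**Conclusion.** The concern holds conditionally. If the one stated rule is used for extrapolated wP rates, the interval is always too narrow, because var(log IRR) is added and is never zero. By how much depends on counts that the documents do not give; over the assumed range, real coverage of a nominal 95% interval runs from about 90% down to 3%. For directly counted rates where a child can contribute more than one event, the loss is small to moderate: about 94% to 87% coverage when 10% to 50% of affected children have two events in a stratum.

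This is a should-fix and not a must-fix. No hypothesis is tested, and Section 7.2.9 says that the epidemiological results are not meant to inform decisions directly. The rates still feed the benefit-risk exercise that the project is meant to test, so their stated precision should be right.

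**What to change.** In Section 7.2.8.3:
- Limit the Poisson sentence to directly counted rates, and use child-clustered intervals (robust variance or bootstrap over children) wherever repeat events are counted.
- For extrapolated wP rates, compute the CI on the log scale from var(log IRR) + var(log baseline IR). Add between-database variance when several databases supply the ratio.
- Report next to Table 6 that the ratio's error is common to all databases that borrow it.
- Count one event per episode, using a gap fixed in advance for each outcome, so that revisits after a window do not enter the SCCS baseline.

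The cost is a few sentences and a little more code. The stated intervals will be wider.
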